Evaluating a Digital Peer Mentoring Platform With College Student Populations

NCT05764785

August 2, 2023

Investigator Protocol

Study Title

Evaluating the acceptability, feasibility, and efficacy of a digital peer mentoring platform with college student populations

Objectives

- **Purpose:** The purpose of the study is to assess the acceptability, feasibility, and efficacy of the MentorPRO application with three University of Massachusetts (UMB) student support program-Directions for Student Potential (DSP).
 - Main outcomes will include attitudes towards the MentorPRO platform, emotional wellbeing (e.g., anxiety, depression), engagement with a third party mental health app, and academic factors (e.g., academic motivation, academic efficacy)
 - **Research Question 1:** What is the acceptability and feasibility of the MentorPRO mentoring platform?
 - **Research Question 2:** Does mentoring with MentorPRO demonstrate an impact on academic outcomes (i.e., GPA), engagement with a mental health mobile application, and indices of wellbeing (i.e., mental health, connectedness, academic self-efficacy, and overall wellbeing) among a diverse sample of incoming or first year college students?
- **Study design:** Every student in the DSP program this summer (and meets the study eligibility criteria) will be eligible to participate in the study. Students who opt into participation in research activities will complete 2 brief surveys.
- **Study intervention:** MentorPRO is a novel application and web platform for mentoring programs that allows students to set goals, track their challenges, and find just-in time resources, while connecting to a mentor for personalized support and progress monitoring. All students in DSP will be matched with a peer mentor. Students will be assigned to getting MentorPRO (intervention condition) or mentoring as usual (control condition), depending on what DSP cohort they are in (a.m. or p.m. classes).
- **Study endpoints (clinical trials):** All students involved in the DSP summer program will be involved in 6 weeks of academic programming and peer mentoring (June 12th-July 21st), meeting 4 days per week during the summer prior to mentees' first year in college, as well as 3 weeks of post-program peer mentoring (total trial of 9 weeks).

Background

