- The DSP Summer program serves up to 300 incoming students.
- At the end of the study, mentors will also be recruited for participation. The estimated number of mentors is 10.
- The number of students who opt into the research activities are expected to be lower than the total number of students in the program.

Setting

- **Sites/locations:**
 - The current study will include an evaluation of the MentorPRO app with DSP.
 - Participants will be involved in an already-established mentoring program through UMB, and will be recruited for additional evaluation efforts from the already-established program.
 - All data collection will occur via online platforms. MentorPRO collects various data points from users directly through the app, including but not limited to: responses to in-app surveys and check-ins, in-app chat messaging, and app engagement. For the students who opt into additional research activities, all surveys will be conducted via UMass Boston's Qualtrics.
- **Prior approvals:** N/A
- **External IRB/ethics review:** N/A
- **Local permissions/local context:** N/A

Recruitment Methods

- **Recruitment process:** During the DSP programming, DSP staff will hand out postcards that has information about the study and a QR code to sign up (Qualtrics). The Qualtrics link will have (in order): an informed consent, an eligibility screener, and if eligible, the pre-intervention survey (Time 1; T1).
 - Students will have time to ask questions, and any questions in which program staff cannot answer will be escalated to the research team. Individuals will also be provided the contact information of the study Principal Investigator ([name]) in the consent form so that they can ask any questions before consenting, if relevant.
- **Recruitment materials:** During the DSP programming, DSP staff will hand out postcards that have information about the study and a QR code to sign up on (Qualtrics). See attached.

Investigator Protocol

- **Screening for eligibility:** All interested participants will be required to take a brief eligibility screening via Qualtrics. If a student does not meet the criteria, the Qualtrics survey will close and not let them proceed with the study. The only inclusion criteria for the current evaluation includes:
 - 18 years of age or older
 - Being a current member of DSP
 - Can speak, read, and write in English
 - Has access to a smartphone
 -

Procedures Involved

- **Study procedures:**
 - **Student mentees:**

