 - All interested participants will read and sign an informed consent, after having time to ask questions to program staff and the research team. Then, they will complete an eligibility screener, and if eligible will complete the rest of the baseline survey.
 - Interested participants will then be prompted to take the first survey after consenting to the study (T1). Students will complete the DSP course for 6 weeks, and will receive peer mentoring during that time. For 3 weeks after the course, students will be able to contact their peer mentor with questions. At the end of the 9-week trial, students will receive a final survey (T2). The eligibility screener, informed consent, and the surveys will be administered via a Qualtrics link. At the conclusion of their participation, all participants will receive a debriefing statement explaining the study and where to find additional resources if needed.
 - Students will be assigned to the intervention or control condition based on what DSP cohort they are part of (a.m. or p.m. classes - the a.m. cohort will be assigned to the intervention/MentorPRO condition, while the p.m. cohort receives mentoring as usual).
 - Mentors will be matched with students who are assigned to both conditions, and therefore all mentors will receive all training materials. In addition to the training in program policies and relationship building provided to program peer mentors, all mentors will undergo training designed by the research team. Mentors will complete a brief orientation to the MentorPROUMB technology, followed by a 30-min interactive online course on providing supportive accountability, through MentorPRO UMB Academy which includes “knowledge checks” to ensure mentors are engaged and understanding the material and tracks progress to ensure course completion. Finally, mentees will be given access to an online orientation to MentorPRO UMB, which walks them

Investigator Protocol

through instructions about how to download and use the app. All study participants (mentors and student mentees) will have access to tech support within 24 hours from Academic Web Pages for any questions or issues that arise.

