- o Because students in the **MentorPRO** condition are being asked to do additional tasks (compared to students who are not in the MentorPRO condition), students in the MentorPRO condition will be allowed to participate in a raffle for a MacBook Air (valued at \$899) for the use of MentorPRO. Students in the MentorPRO condition are being asked to use MentorPRO and the Healthy Minds every day, resulting in up to 35 minutes of effort a day. Given this effort, we feel that this opportunity is adequate compensation. If all participants earn a similar number of chances, the probability of winning the MacBook Air is 1/25 (4 % chance).
 - 5 entries for messaging with their Peer Navigator each week through Aug 11
 - Now through July 28
 - July 28-Aug 4
 - Aug 5 - Aug 11
 - 1 entry for each Check-In before Aug 11
 - 5 entries downloading/installing/following directions to get onto Healthy Minds
 - 1 entry for every day of Healthy Minds use after initial use

Students in the MentorPRO condition *who have already consented to the study* will be informed of the raffle via text, email, and/or phone call and will be given the raffle information, including the attached PDFs (explaining the raffle, and how to get started with Healthy Minds). Questions will be answered by research staff.

Data Analysis

- **Data analysis:** The data will be analyzed both quantitatively and qualitatively. The procedures are outlined below to address each of the research questions:
 - o Research Question 1: What is the acceptability and feasibility of the MentorPRO mentoring program?
 - Recruitment, retention, and adherence to the MentorPRO mentoring program and application will be evaluated to determine the acceptability and feasibility of the program.
 - Acceptability of MentorPRO will also be assessed through open-ended questions and surveys commonly used to evaluate online programs.
 - Qualitative analyses will be conducted to evaluate the level of participants' engagement with mentors via the in-app chat messaging feature.
 - Mentors' responses to survey questions will examine initial mentor feasibility and acceptability of MentorPRO.
 - o Research Question 2: Does mentoring with MentorPRO demonstrate an impact on efficacy for student academic outcomes (i.e., GPA) and indices of wellbeing (i.e., mental health, connectedness, academic self-efficacy,

Investigator Protocol

and overall wellbeing) among a diverse sample of incoming or first year college students?

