 - Exploratory analyses will also be conducted on the data to examine whether other trends or patterns emerge from the data.
- **Data integrity:**
 - In order to ensure quality control of the data collected via the Qualtrics survey, participants will be prevented from submitting multiple responses by enabling this feature within Qualtrics. Data will be checked for missingness.

The final Clinical Trials report findings will follow this analytic plan. We will report descriptive statistics for the sample and primary and secondary outcome measures. Power analysis will be performed to determine that the sample size is adequate to detect a statistically significant difference given the anticipated effect size. Using intention-to-treat analyses, we will conduct repeated measures ANOVAs with two time points (pre and post summer bridge program), to examine whether significant interactions emerge between time and assigned condition (MentorPRO vs. control) on main outcome measures (depression [PHQ-9] and anxiety [GAD-7])

self-reported symptoms and overall wellbeing) and secondary outcome measures (academic self-efficacy, sense of belonging to the university, and cognitive load). To correct for multiple comparisons, we will use a Bonferroni correction, $\alpha = .05$ divided by six tests, resulting in a final α of .008.

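### Bonferroni at .008 for six outcomes is valid, but Holm's step-down keeps every rejection at the same 5% family-wise error and sometimes adds more: a cheap, optional improvement

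*SAP*

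**What the plan says.** The final paragraph of the SAP plans one repeated-measures ANOVA per outcome and tests the time-by-condition interaction.

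- Main outcomes: the text lists "main outcome measures (depression [PHQ-9] and anxiety [GAD-7" scores, then overall wellbeing, which makes three.
- Secondary outcomes: "secondary outcome measures (academic self-efficacy, sense of belonging to the university, and cognitive load", also three.
- Multiplicity: "To correct for multiple comparisons, we will use a Bonferroni correction", with .05 "divided by six tests, resulting in a final α of .008".

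The count of six matches the list. No ordering, gatekeeping or step-down is described, so main and secondary outcomes face the same threshold.

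Neither document gives a target sample size or an effect size for this contrast; the SAP leaves the power analysis to be done. The Protocol says under Number of Participants that "The DSP Summer program serves up to 300 incoming students" and that fewer will opt in. Its raffle text, which applies to the MentorPRO arm only, states that "the probability of winning the MacBook Air is 1/25 (4 % chance" if chances are spread evenly.

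**The concern.** Single-step Bonferroni holds all six tests to the strictest threshold even after some hypotheses have been rejected. Holm relaxes the threshold step by step without giving up family-wise control and without any added assumption. For deciding which outcomes are significant, the SAP's rule therefore never does better than Holm and sometimes does worse.

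The study hopes for benefit across symptoms and wellbeing together, which is the setting in which a step-down gains. The raffle odds suggest a MentorPRO arm of about 25, so avoidable loss of power is worth a sentence. At stake is whether a second or third responding outcome is declared significant. The validity of the analysis is not in question.

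**Working it through.** **1. The SAP's figure.** .05/6 = .00833, which is .008 to three decimals. Rounding down is slightly conservative: 6 × .008 = .048, which bounds the family-wise error under any dependence. For independent tests it is 1 − (1 − .008)^6 = .0471 (.0490 at .00833), against 1 − .95^6 = .265 uncorrected. The rule reproduces and is valid.

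**2. Holm.** Order the six p-values and compare the i-th smallest with .05/(6 − i + 1), stopping at the first failure. The thresholds are .00833, .0100, .0125, .0167, .0250 and .0500. None is below .008, so any p-value at or below .008 is still rejected. This needs no assumption about sample size, effect or correlation.

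**3. Size of the gain.** The documents do not supply the inputs, so these are assumptions:

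- 25 v 25 students. The 25 is inferred from the raffle odds; the control-arm size is not stated.
- A change-score t-test, equivalent to the two-time-point interaction test.
- Pre-post correlation 0.6, giving a standardised change effect of d/√(2(1 − 0.6)) = d/√0.8.
- Outcome correlation 0.5.
- d from 0.3 to 0.8. The Protocol's g=0.45 is for peer mentoring overall, whereas here "All students in DSP will be matched with a peer mentor", so it is not an estimate for this contrast.

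Average power per real effect, from 40,000 simulated trials per scenario:

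| d | Six real: .008 → Holm | Three main real: .008 → Holm |
|---|---|---|
| 0.3 | 6.5% → 8.0% | 6.6% → 7.2% |
| 0.45 | 17% → 22% | 17.5% → 19.0% |
| 0.6 | 36% → 45% | 36% → 39% |
| 0.8 | 65% → 77% | 65% → 69% |

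- Three main effects real at d=0.8: the chance that all three are significant rises from 40% to 48%.
- One real effect: the gain is under 1 point.
- Chance of at least one significant result (six real, d=0.45): 48.2% at .008, 48.9% at .05/6, 48.9% with Holm. Only the rounding matters.
- No rejection was lost in any scenario. Family-wise error with no real effects was .042 at .008 and .043 with Holm.

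**4. Exact check at 25 v 25.** The noncentrality is (d/√0.8) × √(25 × 25/50), which is 1.78 at d=0.45 and 3.16 at d=0.8, on 48 degrees of freedom. Power at .008 is 17.4% and 65.3%; at .05/6 it is 17.8% and 65.9%. An uncorrected .05 test at d=0.45 has 41.4%, so sample size is the main limit.

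**5. Sensitivity.** Gain in percentage points at d = 0.45 / 0.6 / 0.8:

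| MentorPRO v control | Three main real | Six real |
|---|---|---|
| 25 v 15 | 1.1 / 2.1 / 3.4 | 2.9 / 6.4 / 11.2 |
| 25 v 25 | 1.5 / 2.9 / 3.6 | 4.5 / 9.0 / 11.9 |
| 25 v 50 | 2.1 / 3.5 / 3.0 | 6.7 / 10.9 / 8.9 |
| 25 v 100 | 2.6 / 3.6 / 2.1 | 8.1 / 11.3 / 6.0 |

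With outcome correlation 0.2 or 0.7 (three real, 25 v 25), the gain is 1.3 to 4.0 points at d=0.45 and 0.8. The pre-post correlation was not varied.

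**The case against.** The SAP's rule is prespecified, transparent and correct, so replacing it with another valid procedure can be called preference. Several points support that view.

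- **Few conclusions change.** In the same model, Holm alters the set of significant outcomes in about 1% of trials with one real effect. With three real effects it does so in about 5% at d=0.45 and 9% at d=0.6. At d=0.45 with three real effects, 64% of trials have no rejection at .008, so there is usually nothing to step down from. The largest gains need all six effects to be real and sizeable, which the documents do not support. This stands, and it is why the point is rated low.
- **Intervals.** Bonferroni has simple matching simultaneous intervals (99.2%); Holm's are less direct. This is a real cost. It means Holm is uniformly better for the test decisions only.
- **A larger lever exists.** Testing the three main outcomes first, with Holm among them, would raise main-outcome power at d=0.45 (three main effects real) to about 30%, against 17% and 19%. That is true, but it demotes the secondary outcomes and is a separate trade-off. Holm over six costs no outcome anything.
- **Timing.** The SAP describes its second time point as after the bridge program, whose taught part ended July 21, before the SAP date of August 2, 2023. The Protocol's Study procedures differ: "At the end of the 9-week trial, students will receive a final survey (T2". Nine weeks from June 12 is August 14. The doubt is fair, so the change must be conditional on outcome data by arm being unseen.
- **Inputs.** The SAP requires elevated symptoms and the Protocol's criteria do not, so the analysed arm could be smaller than the raffle pool. This affects the size of the gain. It does not affect the result that no rejection is lost.

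**Conclusion.** The concern holds as a low-severity improvement. The Bonferroni rule is valid for the six listed tests. Holm at family-wise .05 makes every rejection it makes, sometimes more, with no further assumption. That part is mathematical.

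The size is conditional. With a MentorPRO arm of 25, control arms of 15 to 100 and d from 0.45 to 0.8, the gain in average power is about 1 to 4 points with three real effects and 3 to 12 points with six. With one real effect (25 v 25) it is negligible. Arm sizes, effect sizes and both correlations are assumptions.

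Holm does not repair low power. It also does not bear on cohort-based allocation or on analyses outside the six tests, such as GPA and engagement.

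**What to change.** If outcome data by arm have not been seen, replace the Bonferroni sentence with:

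> The six p-values will be tested with Holm's step-down procedure at family-wise alpha .05 (ordered p-values compared with .05/6, .05/5, ..., .05), and Holm-adjusted p-values reported. Confidence intervals are unadjusted and will be labelled as such.

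The cost is one SAP passage and no new data. The label is needed because an unadjusted interval can exclude zero when the Holm-adjusted p-value is not significant. With three real effects at d=0.45 and 25 per arm, this happens for at least one outcome in about 56% of simulated trials. If outcome data by arm have already been seen, the prespecified Bonferroni rule should stand.
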